Modified World Mental Health Composite International Diagnostic Interview (CIDI) for Drug Use Disorders Revised. The updated version of the CIDI-2¹⁰⁷ (termed the World Mental Health CIDI [www.hcp.med.harvard.edu/wmhcdi/index.php]) will be used to determine whether individuals met the DSM-5 criteria for opioid and cocaine use disorders or remission during the one-month period prior to the 3, 6, and 12 month study assessments. The CIDI-2 was recommended by an expert panel of the NIDA CTN for gauging DSM-IV remission in clinical studies.¹⁰⁸ Its items can be used to determine DSM-5 criteria for substance use disorders. It will provide important and novel data that is complementary to self-reported drug use and urine testing data, and to the quality of life measurement, as an additional measure of change in functioning. It has been shown to have excellent reliability in diagnosing individuals with drug dependence.¹⁰⁹

Arrests and Incarcerations: In addition to self-reports, the official arrest and incarceration records will be obtained for 1 year prior and 1 year post-study enrollment from the Maryland Department of Public Safety and Correctional Services. These records can be used to gauge the severity of offenses, which may change even when arrest frequency remains about the same. We have successfully obtained and analyzed data of this nature in previous research.¹⁸

Risk Assessment Battery (RAB): The RAB is a brief questionnaire composed of 45 questions covering substance use and sexual HIV risk behaviors that has been extensively used with drug-dependent populations.¹³ The scale's drug-use risk and sex risk scores will be used as outcome measures.

World Health Organization Quality of Life (WHOQOL-BREF) is a brief 32-item instrument developed by the World Health Organization that has been used in a wide variety of populations internationally (Noerholm et al., 2004^{109c}; WHOQOL GROUP, 1998^{109d}; World Health Organization, 2004^{109e}) and has been found to have strong psychometric properties (O'Carroll et al., 2000^{109f}; Skevington et al., 2004^{109g}). The WHOQOL-BREF produces scores in four QOL domains: physical, psychological, social, and environmental. The WHOQOL-BREF also contains a single item, which is not incorporated into any of the four scale scores, asking participants to rate their overall QoL on a 5-point scale from very poor to very good.

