Explanatory Variables. The predictor variables in all statistical models can be categorized as either Treatment Variables, Moderator Variables, or Control Variables.

Treatment Variables: There will be a single treatment variable with three conditions: Intervention Condition [IM+PN v. IM Alone v. Methadone Detoxification (ETAU)].

Moderator Variables: There will be a single moderator variable: Participant Gender.

Control Variables: Three additional predictor variables – participant age, prior methadone maintenance treatment (yes v. no), and self-reported cocaine use at baseline – will be included as “main effects” in all analyses in order to examine for potential differences in treatment outcome as a function of these three variables. (In the parent study: 56% had never previously been in MM treatment; and, self-reported cocaine use at baseline predicted lower treatment retention at 6 months).

Time: Finally, the “repeated factor” in the statistical analysis of all outcome variables measured repeatedly will be assessment Time point, which will allow for the evaluation of both *differential course and impact* of the interventions as a function of the “between-subjects” Treatment Condition factor. (For information regarding which outcome variables are measured at what assessment time points, see **Figure 1. Outcomes and Measures by Aim and Measures**, above).

Planned Contrasts: It is possible to construct two orthogonal, single-degree-of-freedom, planned contrasts that directly test **Hypothesis 1A** and **1B**, respectively. Contrast 1A will compare the two IM treatment conditions (IM+PN and IM Alone, pooled) to the Methadone Detoxification condition. Thus, this comparison directly addresses the question of the differential effectiveness of some form of IM treatment in comparison to a ‘minimally sufficient’ treatment-as-usual (methadone detoxification). Contrast 1B will compare the IM+PN condition to the IM alone condition. Hence, this comparison directly addresses the question of the relative

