Assuming $\alpha=.01$ and $N=300$, the resulting SAS GLIMMIX power estimates ($1 - \beta$) for the four planned contrasts X Time (see *Planned Contrasts*, above; for retained in treatment and arrest and incarceration, the effect of interest was necessarily the four planned contrasts themselves, as there was no Time effect for this outcome) associated with **Hypothesis 1A, 1B, 2A, and 2B** exceeded .81 in all cases, assuming “small” differences associated with each such effect, and even assuming an unstructured covariance matrix. For the set correlation approach, and in this case assuming $N=270$ due to attrition (see *Follow-up and Attrition*, above) in order to remain conservative, an effect size in the population associated with a Planned Contrast X Time for **Hypothesis 1A, 1B, 2A, and 2B** of $f^2=.048$ (.094 for retained in treatment and arrest and incarceration) would yield a power of .9 for that effect. [All 4 Planned Contrasts X Time for **Hypothesis 1A, 1B, 2A, and 2B** have the same degrees of freedom, so yield a common effect size.] The effect size involving the Time effect falls in the “small” range, while the effect size that does not include a Time effect falls in the “small-to-medium” range, with $f^2=.02$ considered a “small” effect and $f^2 = .15$ a “medium” effect.¹²¹

9. Process Evaluation.

9.a. Need for Process Data: Due to the key role of PN in this study for overcoming barriers associated with community re-entry (**Aim 1**), particularly for women (**Aim 2**), we will conduct a qualitative process evaluation that will examine PN experiences in detail.

9.b. Qualitative Sample Selection: Using purposive sampling, a subset of 32 participants (16 IM+PN and 16 IM alone) will be selected to complete semi-structured qualitative interviews. Participant selection will emphasize heterogeneity in order to examine the views and experiences from as diverse a sub-sample as possible and will include an equal number of men and women from each condition. The proposed sample size will ensure that saturation is likely to be achieved (i.e., bringing new participants into the study until the data set is complete, as indicated by data replication or redundancy) and should allow for the extraction of thick, rich data

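### Prior-year arrest and incarceration records are collected but enter none of the stated models for those outcomes, which gives up precision without biasing the comparison

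*Combined protocol and SAP*

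**What the plan says.** Under Measures for Aim 1 and 2 (Arrests and Incarcerations), and again under Human Subjects, the plan says that "the official arrest and incarceration records will be obtained for 1 year prior and 1 year post-study enrollment". The one use it names for these records is severity: "These records can be used to gauge the severity of offenses, which may change even when arrest frequency remains about the same". Figure 1 marks arrests and incarcerations at baseline and at 12 months, for Aims 1-2 and again for Aim 3.

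The Explanatory Variables text sets the predictors for every model. These are the three-level treatment variable, gender ("There will be a single moderator variable: Participant Gender"), Time for outcomes measured repeatedly, and three control variables: "participant age, prior methadone maintenance treatment (yes v. no), and self-reported cocaine use at baseline". Criminal history is not among them.

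The Power section takes the planned contrasts themselves, not their interaction with Time, as the effect of interest for treatment retention and for arrest and incarceration, "as there was no Time effect for this outcome".

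**The concern.** The pre-enrolment value of an outcome is usually among its best available predictors, and adjusting for it is the ordinary way to sharpen a randomised comparison. Here that value will be on file for arrests and for incarceration, but the stated analysis has no place for it.

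Arrest and days of incarceration are named in Aim 1 and in Hypotheses 1A and 1B, and the official records cover a single post-enrolment year, so these outcomes get no help from repeated follow-up measurements. Randomisation is blocked within gender only (section 5), so the design does not balance criminal history beyond what chance provides. At stake are wider intervals than the data require and more exposure to chance imbalance in prior arrests. The validity of the comparison is not at stake.

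**Working it through.** **1. Could the prior year enter by any stated route?**
- As a control variable: no. The list is closed at three, and none is a measure of arrest or custody.
- As a moderator: no. Gender is the only one.
- As the first level of Time: the repeated-measures text refers to Figure 1, which has a baseline mark. The Power section, the only text that says how these outcomes are tested, excludes Time for them.

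**2. The plan's own figure for these outcomes.** The Power section gives f² = .094 for power .9 with alpha .01 and N = 270. The contrasts have one degree of freedom. Take u = 1, assume 9 other model degrees of freedom, so v = 270 - 9 - 1 = 260, and lambda = f²(u + v + 1) = .094 × 262 = 24.6. The noncentral F then gives power .991, not .9; power .9 needs f² of only about .057. The figure does not reproduce. That is a separate matter, and nothing below uses it.

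**3. Gain on a normal-model approximation.** Inputs: 270 analysed (Power section), equal allocation, hence 90 per arm; alpha .01, taken as two-sided. The correlation r between prior-year and post-year values, beyond the existing covariates, is assumed. Formulas:
- residual variance factor = 1 - r²
- equivalent N = 270 / (1 - r²)
- detectable difference at 90% power, in SD units = (2.576 + 1.282) × √(1 - r²) × √(1/n1 + 1/n2)
- power at an assumed difference of 0.4 SD = Φ(0.4 / [√(1 - r²) × √(1/n1 + 1/n2)] - 2.576)

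Contrast 1A is 180 v 90 and Contrast 1B is 90 v 90. Example at r = .3: 1 - .09 = .91, and 270/.91 = 297.

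| Assumed r | 1 - r² | Equivalent N | Detectable 1A | Detectable 1B | Power 1A | Power 1B |
|---|---|---|---|---|---|---|
| 0 | 1 | 270 | 0.498 | 0.575 | .70 | .54 |
| .2 | .96 | 281 | 0.488 | 0.563 | .72 | .57 |
| .3 | .91 | 297 | 0.475 | 0.549 | .75 | .59 |
| .4 | .84 | 321 | 0.456 | 0.527 | .79 | .64 |
| .5 | .75 | 360 | 0.431 | 0.498 | .84 | .70 |

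The 270 reflects interview attrition. Official records may be available for more of the 300, but the percentage reductions in variance do not depend on N.

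**4. Check on counts.** The plan models counts as Poisson or negative binomial, so the formula above is only a guide. A simulation used overdispersed Poisson arrests with lognormal person-level rates, a mean of 1 arrest per year, the same underlying rate in both years, a rate ratio of .65, 180 v 90, and quasi-Poisson regression with and without log(prior count + 0.5), at alpha .01. There were 400 replicates per row, so the simulation error is about 2.5 points. All of these settings are assumptions.

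| Correlation of counts | Power without | Power with | Mean SE without | Mean SE with |
|---|---|---|---|---|
| .08 | .66 | .65 | .145 | .145 |
| .30 | .55 | .59 | .162 | .156 |
| .52 | .36 | .49 | .195 | .168 |

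Overdispersion rises down the table, so compare within rows only. At .30 the squared ratio of standard errors is (.156/.162)² = .93, a 7% reduction against 9% from the formula, and the power gain is not far above simulation error. At .08 there is no gain. At .52 the gain is clear. Days incarcerated were not simulated.

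**The case against.** The best defence is that the plan already uses the prior year. Time applies to outcomes measured repeatedly, the reader is sent to Figure 1 to see which those are, and Figure 1 marks arrests and incarcerations at baseline as well as at 12 months. On that reading the prior year is the first Time level, and the remark in the Power section only describes what was simulated. This shows a real tension in the documents. It does not settle it in the plan's favour, because the Power section is the only place that says how these outcomes are tested and it excludes Time. If a pre/post Time factor was intended, the plan still has to say so.

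The second defence is that the benefit is unknown, and this stands. No correlation is given, the relevant one is that left after gender, age, prior methadone maintenance and cocaine use, and at low values the gain for counts is negligible.

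The third is that adjustment is not free of complications, and this also stands. Everyone enrols while detained and the window is anchored at enrolment, so the prior year contains the index arrest and part of the index detention, and the post-enrolment year can open with the rest of it. If arrest is analysed as yes/no by logistic regression, the adjusted effect is conditional on the covariate and is a different quantity from the unadjusted one.

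**Conclusion.** The point holds as a missed efficiency. As the analysis is stated, the prior-year value has no role in the arrest or incarceration models. The randomised contrasts remain unbiased. The gain from adding it is 4% to 25% of residual variance for assumed r of .2 to .5 on a normal model. For counts it is less certain, and little or none at low r.

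Three stronger inferences are tempting but not supported.
- A reader might infer from f² = .094 that these outcomes have the weakest power in the plan. That value is shared with treatment retention, and it corresponds to power of about .99, not .9, under the plan's own degrees of freedom, alpha and N.
- A reader might infer that arrests and incarceration drive the cost-benefit analysis. Hypothesis 3c lists criminal activity beside health care use and employment, and the Progress Report attributes the main cost-benefit difference in the parent trial to treatment cost, with no significant difference in arrests or days of incarceration.
- A reader might infer that the change has no downside. The index-event definition and the conditional effect in a logistic model are small costs, but they are real.

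**What to change.** Before outcomes by arm are seen, prespecify the following:
- In the arrest model, add the prior-year official arrest count, for example as log(1 + count), excluding the index arrest.
- In the incarceration model, add prior-year days incarcerated from the same records, excluding index detention days.
- Keep gender and the three existing control variables in both.
- State that this covariate replaces any baseline Time level implied by Figure 1.
- Define the index arrest and index detention, and say how any index detention remaining after enrolment is counted in the outcome year, identically for all arms.
- If arrest is analysed as a binary outcome by logistic regression, say that the reported effect is conditional on the covariates.

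The cost is a short addition to the analysis text plus the index-event definitions. The records are already being obtained, so no further data collection or visits are needed.

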Arrest and incarceration (Criminal Justice Records)	◆	12-months only

* Participants transitioning directly to other community MMPs or buprenorphine treatment will be considered still in treatment.

† Consistent with prior research, the SASCAP will be administered once during the treatment phase.

Participants will be paid \$30 for follow-up interviews (regardless of whether they are conducted in the community or during a re-incarceration) and will provide consent for research staff to check hospital and arrest records. Participants who are interviewed for follow-up during a re-incarceration will have the option to receive their \$30 deposited into their jail or prison account or to have a money order mailed to a designated person. They will not be paid for the baseline interview conducted in jail to avoid the perception of coercion.

Longer-term follow-ups: Participants will be asked (using a consent form addendum) if they'd be willing to have a 24-month follow-up interview for which they would be paid \$40. The 24-month interviews will include the same assessments as the 12-month interviews described above. In addition they will be asked if the research team could contact them beyond the 24-month follow-up for further informed consent for even longer-term follow-up interviews.

Measures for Aim 1 and 2:

Entry into Treatment: within the first 30 days of release from jail will be obtained from patient self-report from the Methadone Treatment Exposure form.

Enrollment in Treatment: will also be obtained from self-report on the Methadone Treatment Exposure form.

Addiction Severity Index (ASI): assesses patient functioning through a 30-45 minute interview covering 7 key domains over the past 30 days including drug and alcohol use, legal, medical, psychiatric and employment status, family functioning and social relations.¹⁰⁶ Composite scores and items from each domain will be investigated (with particular emphasis on drug use and legal scores and items).

Urine Drug Testing: Urine samples will be collected by project staff at 1, 3, 6, and 12 months post-baseline and tested by an approved rapid drug test cup for opiates, methadone, buprenorphine, cocaine, and benzodiazepines. Results will be used for research purposes only and will not be shared with clinic staff.

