Substance Abuse Services Cost Analysis Program (SASCAP): Costs for each of the study conditions will be estimated using an activity-based costing approach which will allow cost estimation at the service level for study participants. To collect resource use and cost data necessary for activity-based costing, we will modify the SASCAP⁹⁰ to collect resource use and cost data for each condition necessary for activity-based costing. The SASCAP consists of a provider questionnaire administered once during the intervention phase to collect activity-level resource use and cost data for provider staff and nonlabor resources such as contracted services, building space, supplies and materials, and other miscellaneous resources (e.g., utilities). The SASCAP method reliably estimates the costs of specific treatment activities and the total cost per patient, and the investigators [name] and [name] have applied this micro-costing approach in other treatment studies.^{66,89,114,115} If a significant number of participants transition from the initial MMP to another MMP or buprenorphine treatment, costs for these treatments will also be determined.

AIM 1. To determine the relative effectiveness of IM+PN v. IM alone v. brief methadone detoxification (enhanced treatment-as-usual [ETAU]) for opioid-dependent detainees at 1, 3, 6, and 12 months post-release in terms of: (a) post-release treatment entry and retention; (b) illicit opioid and cocaine use; (c) meeting DSM-5 criteria of opioid and cocaine dependence; (d) HIV-risk behavior; and (e) criminal behavior, arrest, and days of incarceration.

Hypothesis 1A: The IM+PN and IM Alone conditions will have higher rates of treatment entry and longer retention, and concomitant lower rates of illicit opioid and cocaine use and of meeting DSM-5 criteria for opioid and cocaine use disorders, HIV risk behavior, criminal behavior, arrests, and days of incarcerations than will the Methadone Detoxification [ETAU] condition.

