effectiveness of the adding PN to IM treatment. Similarly, it is possible to construct two orthogonal, single-degree-of-freedom, planned contrasts that directly test **Hypothesis 2A** and **2B**, respectively. Contrast 2A will compare males and females in the IM+PN condition. Hence, this comparison directly addresses the question of the differential effectiveness of IM+PN treatment for males and females. Contrast 2B will compare males and females in the IM Alone and Methadone Detoxification conditions, pooled. Thus, this comparison directly addresses the question of the differential effectiveness of non-PN treatments for males and females. Given that both the course and impact of treatment are important to evaluate, planned contrasts can be examined both as each interacts with the “repeated factor” of Time (when there is a repeated factor), and as a “simple effect” at a given time point, in the event either Contrast X Time interaction effect proves to be significant.

AIM 3: To conduct a focused cost-effectiveness and cost-benefit study of the three treatment conditions

HYPOTHESIS 3a (Cost Hypothesis). IM alone will have greater treatment costs per person than detoxification. Furthermore, IM+PN will have greater treatment costs per person than IM alone.

HYPOTHESIS 3b (Cost-Effectiveness Hypothesis). IM+PN will yield better outcomes relative to the IM alone which in turn will yield better outcomes than detoxification in terms of higher rates of treatment entry and longer retention in treatment, and greater reductions in illicit opioid and cocaine use, decreased likelihood of meeting DSM-5 criteria for opioid and cocaine use disorders, decreased HIV risk behavior, and decreased criminal behavior, arrest, and incarceration. The better outcomes for IM+PN justify the greater costs of IM+PN compared to IM alone, making IM+PN cost effective compared to IM alone.

HYPOTHESIS 3c (Cost-Benefit Hypothesis). IM alone will yield greater economic benefit in terms of criminal activity, health care utilization, and employment in the 12-month post-release period relative to its costs relative to the detoxification condition. Furthermore, IM+PN will yield greater economic benefits than IM alone.

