Consenting opioid-dependent detainee participants will be interviewed four times, at study entry during detention (baseline) and at 1,3, 6, and 12 months post-release while in the community. Participants will receive \$30 for each of the three assessments in the community for a possible total of \$120. No payment will be provided for the baseline interview in the detention center because this could be considered coercive given the financial constraints of incarcerated individuals. However, participants who are re-incarcerated may participate in follow-up interviews, in which case, they will have the option of receiving their \$30 payment deposited in their jail or prison account or to have it mailed to a person of their choice. The 32 participants who participate in the qualitative interviews will receive an additional \$30 per each of two interviews for a potential total of an additional \$60. Follow-up qualitative interviews will not be conducted for re-incarcerated participants because it will not be possible to bring a recorder into the correctional institutions. In addition, participants providing a signed informed consent addendum will be interviewed at 24-months following enrollment and receive \$40 for completing that interview.

The patient navigators will not receive payment for their interview because they will be interviewed during regular working hours.

The following instruments will be used to obtain information from the 300 opioid-dependent participants:

Addiction Severity Index (ASI): assesses patient functioning through a 30 -45 minute interview covering 7 key domains over the past 30 days including drug and alcohol use, legal, medical, psychiatric and employment status, family functioning and social relations.¹⁰⁶

Urine Drug Testing: Urine samples will be collected by project staff at 3 and 12 months post-baseline and tested by an approved rapid drug test cup for opiates, methadone, buprenorphine, cocaine, and benzodiazepines. These results will be used for research purposes only and will not be shared with clinic staff.

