Modified World Mental Health Composite International Diagnostic Interview (CIDI) for Drug Use Disorders. The updated version of the CIDI-2¹⁰⁷ (termed the World Mental Health CIDI [www.hcp.med.harvard.edu/wmhcdi/index.php]) will be used to determine whether individuals met the DSM-V criteria for opioid and cocaine dependence or remission during the one month period prior to the 3, 6, and 12-month assessments. The CIDI-2 was recommended by an expert panel of the NIDA CTN for gauging DSM-IV remission in clinical studies.¹⁰⁸ It has been shown to have excellent reliability in diagnosing individuals with drug dependence.¹⁰⁹ Its items can be used to determine DSM-5 criteria for substance use disorders.

Arrest and Incarcerations: In addition to self-reports, the official arrest and incarceration records will be obtained for 1 year prior and 1 year post-study enrollment from the Maryland Department of Public Safety and Correctional Services. These records can be used to gauge the severity of offenses, which may change even when arrest frequency remains about the same.

Risk Assessment Battery (RAB): The RAB is a brief questionnaire composed of 45 questions covering substance use and sexual HIV risk behaviors that has been extensively used with drug-dependent populations.¹³ The scale's drug-use risk and sex risk scores will be used as outcome measures.

Overdose AE Form. This brief 12 item questionnaire was devised for the present study to examine the number and characteristics and responses to any non-lethal overdoses between study visits.

Methadone Treatment Exposure Questionnaire. This brief 7 item questionnaire was devised for the present study to examine methadone treatment status, anticipated length of sojourn in methadone treatment, and reasons for leaving treatment (if applicable).

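### Follow-up is timed from baseline in some sections and from release in others, and the official arrest and incarceration records stop one year after in-jail enrolment although the aims cover 12 months after release

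*Combined protocol and SAP*

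**What the plan says.** Baseline and randomization take place in detention. Follow-up is then timed from two different points.

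- **From baseline:** the Abstract, the Project Timeline and both urine paragraphs. Measures for Aim 1 and 2 has "Urine samples will be collected by project staff at 1, 3, 6, and 12 months post-baseline"; Human Subjects has "Urine samples will be collected by project staff at 3 and 12 months post-baseline".
- **From release:** the opening of Specific Study Methods, section 7 (Research Interviews), Aim 1, and Participant Recruitment in Human Subjects. Research Information in Human Subjects places interviews "at study entry during detention (baseline) and at 1,3, 6, and 12 months post-release while in the community", although its own urine paragraph counts from baseline.
- **From enrolment:** the 24-month interview (Human Subjects).
- **No origin given:** Figure 1 and the Time factor in the analysis section.

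Treatment entry "within the first 30 days of release from jail will be obtained from patient self-report", which ties that outcome to release.

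For official data, Measures for Aim 1 and 2 says that "official arrest and incarceration records will be obtained for 1 year prior and 1 year post-study enrollment", and Human Subjects repeats that "records will be obtained for 1 year prior and 1 year post-study enrollment". Aim 1 compares the arms "at 1, 3, 6, and 12 months post-release in terms of" a list that includes arrest and days of incarceration. Hypothesis 3c concerns economic benefit, including from criminal activity, "in the 12-month post-release period".

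**The concern.** Because baseline is in jail, the two origins differ for each participant by the stay remaining after enrolment. A visit label such as 12 months has no fixed meaning until the origin is stated, and the planned contrasts are examined by Time.

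The records window is a separate matter and does not go away once the visit labels are settled. If visits were timed from baseline, the records would match the visits, but neither would match the aims. If visits are timed from release, the records match neither the visits nor the aims. The Power section treats arrest and incarceration as outcomes without a Time factor, so for the official-record source the window largely defines the outcome. The plan also does not say whether days left in the index detention count as days of incarceration.

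At stake are coverage of the outcome period that the aims name, some precision on arrests and re-incarceration, and a choice of outcome window left open until after data are seen.

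**Working it through.** The plan gives no figure for this point, so there is none to reproduce.

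**1. Which origin is meant for visits.** Section 7, which is devoted to the interviews, says release. Research Information puts interviews after release and in the community. Participant Recruitment in Human Subjects says that urine is taken at the community assessments, and Figure 1 lists ASI and urine testing in one row at the same visits. Treatment entry is defined over the 30 days after release and collected at the 1-month visit, which works only if that visit is timed from release. Together these indicate release for interviews and urine alike. The post-baseline labels are then the ones to correct.

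**2. Records coverage.** Let S be the days from enrolment to release. Records end at day 365 after enrolment; the post-release year ends at day 365 + S.

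- Post-release days covered = 365 − S.
- Share of the post-release year lost = S/365.
- Index-detention days inside the post-enrolment records window = S.

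The documents do not give S for participants. Section 2 (Study Sites) gives 42 days as the average stay of all detainees; 10 and 90 days are assumed bounds.

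| S (days) | Post-release days covered | Share lost |
|---|---|---|
| 10 | 355 | 2.7% |
| 42 | 323 | 11.5% |
| 90 | 275 | 24.7% |

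At S = 42, full coverage needs records to day 365 + 42 = 407 after enrolment.

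**3. Precision.** With t = 1 − S/365 (0.973, 0.885, 0.753 at 10, 42 and 90 days), a constant event rate and the same S for everyone, the standard error of a log arrest rate ratio grows as follows.

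- Poisson, factor 1/√t: 1.014, 1.063, 1.152. That is +6.3% at 42 days (range +1.4% to +15.2%).
- Negative binomial, assuming a mean of m = 1 arrest per year and dispersion k = 1, factor √[(1/(mt) + k)/(1/m + k)]: 1.007, 1.032, 1.079. That is +3.2% at 42 days (range +0.7% to +7.9%).

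**4. Direction.** Assignment is random within gender, so the remaining stay should be balanced across arms on average. The lost stretch then falls equally on all arms and is not expected to create a difference between them.

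**The case against.** The strongest reply has four parts.

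- **A window of one year before and one year after enrolment is coherent.** It is symmetric and fits an intent-to-treat analysis from randomization. A release-based window starts at an event after randomization and leaves out anyone never released, against the plan's rule that all participants are analysed. This stands as a reason to keep the from-randomization analysis and not to impose a release-based one as primary. It does not make the window match the aims.
- **Other sources cover the gap.** Figure 1 takes arrests and incarcerations from self-report as well as records, and the Economic Form 90 collects arrests and nights incarcerated. This stands in part. Both depend on follow-up interviews, which the plan expects about 90% of participants to complete.
- **The harm is small.** This stands: the precision loss at 42 days is about 3% to 6% for one data source.
- **The visit labels are loose wording.** Probably so, but nothing in the plan says which labels govern.

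Three stronger readings are tempting but not supported.

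- A reader might infer that urine samples are taken at a different time from the interviews, or that a 1-month visit falls before release (30 − 42 = day −12). The sections compared in step 1 of the working make both unlikely.
- A reader might use the Project Timeline to settle the origin. Enrolment in Months 6 to 28 puts visits in about Months 7 to 40 from baseline, or 8 to 42 from release with a 42-day stay. The stated Months 9 to 42 match the release end date but not its start, and Month 9 also equals Month 6 plus three months. The Timeline is imprecise in itself: it calls Months 41 to 48 five months, and four enrolments a week over about 100 weeks would give about 400, not 300. It settles nothing.
- A reader might infer that index detention dilutes the ratio of incarceration days between arms. That follows only if index days are counted as outcome days, which no section says.

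**Conclusion.** The point holds as a minor one. The conflict between the visit labels and the mismatch between the records window and the aims are both certain from the text. Their size is not, because it depends on a stay after enrolment that the documents do not give. The 42-day figure describes all detainees from entry, not trial participants from enrolment, so the 11.5% is illustrative. The precision figures rest further on a constant event rate, a common stay, and the assumed arrest mean and dispersion. No bias between arms is claimed. What remains is an official-record outcome that does not cover the full period named in Aim 1 and Hypothesis 3c, modest lost precision partly offset by self-report, and no stated rule for index-detention days.

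**What to change.** 1. Bring the Abstract, the two urine paragraphs and the Project Timeline into line with the post-release schedule in Specific Study Methods, section 7, Aim 1 and Participant Recruitment. The two urine paragraphs also list different months and should be aligned in the same edit. State that the 24-month interview is timed from enrolment.
2. In both descriptions of the official records, extend the request to 12 months after each participant's release, or to study close if earlier. Keep the one-year window before enrolment.
3. Report arrests and incarceration days in two ways: from randomization for all 300 (intent-to-treat), and for the 12 months after release as the aims state. Separate index-detention days from re-incarceration days, and use observed days as exposure where follow-up is cut short. The sponsor should choose in advance which version is primary.

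**Cost.** These are text edits plus a later end date on a records request already planned for Months 41 to 48. For someone enrolled at the end of Month 28, the post-release year ends at 28 + 12 + 42/30.4 = 41.4 months with a 42-day stay, or 43.0 months with 90 days. A request at the end of Month 44 would cover stays up to about 4 × 30.4 = 122 days. The consent wording must be checked first: section 4.b names arrest records only, while Participant Recruitment in Human Subjects also names incarceration records. The downsides are unequal follow-up for late releases, and that participants never released contribute only to the from-randomization analysis.
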